#### ***4.2.2 Clinical Experience with Givinostat Including Risks and Benefits***

Completed and updated data that describe the clinical experience with givinostat are reported in Section 6 “Effects in Humans” of the current Investigator Brochure Dossier related to ITF2357.

Givinostat has been tested in a number of clinical studies in adults and paediatric populations. Three major indications have been explored with Givinostat, chronic inflammatory diseases, neuromuscular disorder and oncology. The maximum administered dose was a single dose of 600 mg in healthy volunteers and up to 400 mg once per week in subjects with multiple myeloma. Doses up to approximately 100 mg bid were generally well tolerated in adults. In paediatric subjects, doses up to 0.75 mg/kg bid have been administered for up to 6 months (with 1 additional subject having been treated for 2 years and 7 months) in patients with Juvenile Idiopathic Arthritis. In subjects with DMD enrolled in study DSC/11/2357/43 (i.e., subjects between 7 and 10 years of age at study start), the maximum dose administered in the dose escalation phase was 50 mg bid for up to 2 weeks i.e., while the maximum dose administered for up to 1 year in the second part of the study was 37.5 mg bid. Since, clearance increases with increased weight (see Section 8.2.1) doses have been increased in the extension phase of study DSC/11/2357/43 due to the increase in weight of the enrolled children; as a result the maximum dose administered in this extension phase is 60 mg bid.

The most common AEs observed were thrombocytopenia, as well as gastrointestinal toxicities. Adverse events were generally mild to moderate and reversible upon discontinuation of study drug. Moreover, dose-dependent asymptomatic and reversible platelets count reductions were observed both in healthy volunteers and subjects treated with givinostat. These decreases typically occurred within the first week after treatment initiation, reached a nadir after 2 to 3 weeks of treatment, and then remained at a plateau (see the IB, Section 7). The majority of thrombocytopenic events were mild in severity with fewer than 10% of subjects developing platelets count below  $75 \times 10^9/L$ . All occurrences resolved completely within 2 to 3 weeks of discontinuation of treatment, suggesting a rapidly reversible effect. Overall, sixteen haemorrhagic drug-related AEs were reported by 14 patients

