\* based on average QTc value of triplicate ECGs. For example, if an ECG demonstrates a prolonged QTcF interval >450msec, 2 more ECGs should be obtained over a brief period, and then the averaged QTcF values of the 3 ECGs should be used to determine whether the subjects should be discontinued from the study. If the mean QTcF value of the 3 replicates still meets the stopping criteria the subject has to interrupt the study drug, the medical monitor has to be informed and the value must be confirmed by the central reading before withdraw the subject from the study. The QTc has to be calculated with the Fridericia formula  $QTc = QT/RR^{1/3}$ .

Study drug should be temporarily stopped if any of the following occur:

- moderate or severe diarrhoea (i.e., increase more than 4 stools per day).
- platelets count  $<75 \times 10^9/L$  but  $>50 \times 10^9/L$  (the treatment should be temporarily stopped and platelets count has to be performed by 1 week and re-tested until platelets will be normalized);
- white blood cell  $<3.0 \times 10^9/L$  but  $>2.0 \times 10^9/L$  (the treatment should be temporarily stopped and white blood cells have to be measured by 1 week and re-tested until white blood cells will be normalized);
- hemoglobin  $<10.0$  g/dL but  $> 8.0$  g/dL (the treatment should be temporarily stopped and hemoglobin has to be measured by 1 week and re-tested until hemoglobin will be normalized);
- Triglycerides  $>300$  mg/dL (3.42 mmol/L) in fasting condition (the treatment should be temporarily stopped and triglycerides has to be measured every 2 weeks until triglycerides return to levels below 300 mg/dL (3.42 mmol/L);

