**Dose Modification (all subjects):**

If subjects (i.e. those already in treatment or those who will be randomized under protocol version 6.0 or 7.0 or 8.0) gain weight during the study the drug dose must be kept unchanged.

If subjects (i.e. those already in treatment or those who will be randomized under protocol version 6.0 or 7.0 or 8.0) lose weight during the study, the drug dose should be adjusted

according to Table 2 or Table 3 if the subject is still on treatment at starting dose, or according to Table 4 or Table 5 if the subject has already reduced the starting dose.

All subjects will be asked to have platelets count assessments weekly during the first month of treatment and performed every two weeks during the second month of treatment, in order to strictly monitor this parameter for safety reasons.

If the dose is reduced due to platelet count  $\leq 150 \times 10^9/L$ , and/or white blood cell  $< 3.0 \times 10^9/L$  and/or hemoglobin  $< 10.0 \text{ mg/dL}$  a complete blood count (i.e.CBC) test must be performed weekly for 8 consecutive weeks.

If a dose adjustment and/or modification of schedule of assessments is decided by the Investigator or authorized designee, it is advised to discuss this decision with the Medical Monitor, however this is not mandatory as the Investigator is the only responsible for the medical care of the subject and the Investigator's decision should not be influenced, deleted nor approved by the Medical Monitor.

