2.8 Data presentations

The data will be summarised in tabular form by treatment group apart from disposition of subjects, protocol deviations, background and demographic data, administration of investigational medicinal product (IMP), plasma concentrations of givinostat and its major metabolites, prior and concomitant medications, which will be summarised by treatment group and overall subjects.

Only scheduled post-baseline laboratory, vital signs and electrocardiogram (ECG) values will be tabulated, post-baseline repeat/unscheduled assessments will be listed.

Listings will be sorted by treatment group, subject number and date/time of assessment.

Treatment groups will be presented in the following order: Givinostat, Placebo.

Graphical presentations of the data will also be provided where appropriate.

All efficacy analyses and data summaries will be presented for the target population only. Safety data will only be summarised for the overall subject population. Data summaries for disposition of subjects, protocol deviations, background and demographic data, administration of IMP, ankle range of motion, modified MRC grade and genotype data will be presented for both the target and overall subject populations. Presentation of analyses and summaries of PK data will be discussed in a separate Population PK data analysis plan (see Section 4.5).

Listings will be presented for the overall subject population. Inclusion of each subject in the target or off-target population will be indicated in the listing of analysis set assignments for reference. Listings for efficacy and PK data will also present patients sorted by target or off-target population for each treatment group.

The target population will serve as the basis for any formal analysis of efficacy.

Any further repeats of the data summaries and analyses for target, off-target or overall subject populations may be considered at a later date and included post hoc. Details of any such repeats will be included in a SAP addendum as appropriate.

Where data are imputed according to the rules defined in [Section 4.4.4](#), the imputed data will be used in all data presentations and analyses. Imputed values for efficacy data will be flagged in the listings with an indication of the missing data classification as applicable.

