5.2 Clinical Laboratory Evaluation

For each laboratory parameter, the baseline value will be defined as the last non-missing scheduled or unscheduled value available prior to or on the date of first study treatment. Where the value is recorded on the same date as first study treatment and there is no further information to confirm whether this was prior to start of treatment, the value will be considered prior to treatment if this was a screening or randomisation assessment and otherwise will be considered post treatment. If no measurement is recorded prior to first study treatment administration, the baseline value will be considered missing.

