5.2.1 Hematology

Hematology parameters will be measured in Système International (SI) units at all EU sites and in US conventional units at all US sites. All results will be converted to SI units for the purposes of summaries, plots and listings. Summary statistics of hematology observed values and change from baseline by parameter and visit will be presented by treatment group for all subjects in the safety analysis set.

In addition, the following summaries in relation to post-baseline platelet counts will be presented by treatment group: minimum values, time to nadir (days) and time to recovery (days). These will be defined as follows:

Minimum value = minimum post-baseline platelet count for the subject.

Time to nadir (days) = time to first minimum value post-baseline regardless if this is within the normal range.

Time to recovery (days) = for subjects whose minimum post-baseline value is below the lower limit of normal, the time to recovery is calculated as the time from the minimum value below lower limit of normal to the first value within the normal range.

Furthermore, a table will be presented for subjects in the safety analysis set who reduced dose due to platelet count decrease which will summarise the following in relation to post-baseline platelet counts by treatment group: minimum values, time to nadir (days), time to recovery (days), time on treatment after recovery (days), additional platelet decrease after recovery, time on treatment without recovery (days), where:

Time on treatment after recovery = for subjects who record recovery from the minimum value below the lower limit of normal, the time on treatment after recovery

is calculated as the time from the date of recovery to the last treatment date or date of data cut-off.

Additional platelet decrease after recovery = number of subjects who record recovery from the minimum value below the lower limit of normal and then record a subsequent value below the lower limit of normal.

Time on treatment without recovery = for subjects who do not record recovery from the minimum value below the lower limit of normal, the time on treatment without recovery is calculated from the date of the minimum value below the lower limit of normal to the last treatment date or date of data cut-off.

A plot of the mean platelet count at each visit will be produced by treatment group.

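### SAP 2.8 keeps unscheduled laboratory values out of tables and SAP 5.2.1/5.2.2 make no exception, so read literally the platelet and triglyceride recovery times are overstated, mainly for changes found from Week 12

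*SAP*

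**What the plan says.** SAP 2.8 (Data presentations) sets the general rule: "Only scheduled post-baseline laboratory, vital signs and electrocardiogram (ECG) values will be tabulated, post-baseline repeat/unscheduled assessments will be listed".

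SAP 5.2.1 (Hematology) adds subject-level platelet summaries. The nadir is given as "Minimum value = minimum post-baseline platelet count for the subject". Time to recovery, for boys whose minimum is below the lower limit of normal (LLN), is the "time from the minimum value below lower limit of normal to the first value within the normal range". A second table, "for subjects in the safety analysis set who reduced dose due to platelet count decrease", adds time on treatment after recovery, time on treatment without recovery, and any further decrease after recovery. SAP 5.2.2 repeats the set for triglycerides, with maximum and upper limit in place of minimum and lower limit. Neither section says whether unscheduled values count. Addendum 1 does not address it.

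For the laboratory baseline, SAP 5.2 does say so: the "last non-missing scheduled or unscheduled value available prior to or on the date of first study treatment".

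The protocol orders extra samples once a value is abnormal. Under 7.3.1, a platelet count at or below 50 x 10^9/L is repeated the next working day. Below 75 but above 50, treatment is paused and a "platelets count has to be performed by 1 week and re-tested until platelets will be normalized". Triglycerides above 300 mg/dL are measured every 2 weeks until they fall below that level. Under 8.2.2, after a dose reduction for platelets, white cells or haemoglobin, a complete blood count (CBC) "test must be performed weekly for 8 consecutive weeks".

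**The concern.** Nadir and recovery measures depend on the samples taken around and after an abnormal value. Those are largely the samples that 2.8 sends to listings. Because 5.2 names unscheduled values for baseline and no section does so after baseline, a programmer who follows the text would feed only scheduled records into these tables.

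Platelet reduction is among the most common adverse effects in the protocol's summary of clinical experience (4.2.2). Protocol 8.2.1 reports that roughly 50 to 60% of subjects with at least 8 weeks of treatment had to reduce dose for it, and gives this as the reason for lowering the starting dose. These tables are where a reader will look for the depth and reversibility of the effect. A platelet table is also among the outputs listed for the data monitoring committee (SAP Appendix 7.6).

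**Working it through.** The plan states no figure for this point, so there is none to reproduce. The check is what the sampling schedule allows a table to show.

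**Inputs**
- Scheduled haematology after baseline (Protocol Table 6): Weeks 1, 2, 3, 4, 6, 8, 12, 24, 36, 48, 60, 72.
- Gaps: 7 days up to Week 4, 14 days up to Week 8, 28 days from Week 8 to 12, then 12 x 7 = 84 days. With ±7 days on each visit, the last is 84 ± 14, or 70 to 98 days.
- Assumed time to an in-range count: 14 to 21 days, from Protocol 4.2.2: "All occurrences resolved completely within 2 to 3 weeks of discontinuation of treatment".

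**Recovery time, low count found at a scheduled visit**

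Tabulated recovery = first available sample at or after true recovery, minus the visit date.

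| Low count at | With weekly retests | Scheduled values only |
|---|---|---|
| Weeks 1–4 | 14–21 days | 14–28 days |
| Week 6 | 14–21 days | 14–42 days |
| Week 8 | 14–21 days | 28 days |
| Weeks 12, 24, 36, 48, 60 | 14–21 days | 84 days |

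From Week 12 the ratio is 84/21 = 4 to 84/14 = 6. The excess is 84 − 21 = 63 to 84 − 14 = 70 days, and time on treatment after recovery is shortened by the same amount. For a fixed nadir, removing samples can delay the first in-range value but never bring it forward.

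**How many of the 8 weekly CBCs fall on a scheduled visit**

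| Dose reduced at week | 1 | 2 | 3 | 4 | 6 | 8 | 12 or later |
|---|---|---|---|---|---|---|---|
| Of 8, coinciding | 5 | 4 | 3 | 3 | 2 | 1 | 0 |

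So 3 of 8 are left out after a reduction at Week 1, and all 8 from Week 12.

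**Triglycerides.** Retests are every 14 days, against 84 days between scheduled samples from Week 12.

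**Nadir.** Protocol 4.2.2 puts the usual platelet nadir at 2 to 3 weeks of treatment, inside the weekly scheduled sampling. An illustrative simulation gives a sense of scale. Its assumptions are not from the documents: a V-shaped dip, fall over 7–21 days, rise over 14–21 days, LLN 150 x 10^9/L, 5% measurement noise, and 8 weekly retests after the first low scheduled count. Results are for dips detected at a scheduled visit:

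| Onset | Sampled nadir missed | Recovery overstated | Median recovery, scheduled only vs all values |
|---|---|---|---|
| First 28 days | about 9% | 54% (same in 46%) | 14 vs 7 days |
| After Week 8 | about 17% | essentially all | 84 vs 7 days |

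**The case against.** The strongest reply is that 5.2.1 is silent rather than restrictive. It separates by-visit summaries from subject-level, date-based measures, and a specific definition of each subject's minimum can be read to override a general presentation rule. The table shells, which might settle the input records, are a separate document not available here. This stands: the documents do not show that the tables will certainly omit the retests. But 2.8 is an explicit restriction with no exception, so the conflict needs resolving.

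One could also argue that the weekly CBC counts as scheduled, because it appears in a footnote to the Schedule of Assessments. That is weaker. SAP 2.4 points to Protocol 9.1 for the visit structure and scheduled assessments, and the visit lists there do not contain it.

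Three further points stand:
- Most falls are expected early, when many retests coincide with scheduled visits and the usual nadir is captured.
- The 14 to 21 days is measured from discontinuation, whereas SAP recovery runs from the minimum value. Boys with a persistent count at or below 150 x 10^9/L who do not meet the stopping criteria have the dose reduced, not stopped.
- A reader might infer that the most severe cases disappear. They do not. A confirmed count at or below 50 x 10^9/L means permanent discontinuation and an end-of-study visit with haematology once the event resolves or stabilises (7.3.1, 9.1.8). It should also appear among adverse events leading to discontinuation and in the dose-modification tables.

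All haematology values are listed with abnormal ones flagged, and no hypothesis test is affected. Listings do not correct a summary table, however, and the worst-case summaries mentioned in SAP 2.9 are optional, post hoc and tied to COVID-19.

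**Conclusion.** The point holds as a conflict between an explicit presentation rule and subject-level definitions that need the excluded data. Followed literally, the plan overstates recovery time: by 0 to 7 days for low counts found at Weeks 1–4, up to 21 days at Week 6, 7 to 14 days at Week 8, and 63 to 70 days from Week 12. These sizes assume in-range values at 14 to 21 days and weekly retests. The 4- to 6-fold figure belongs only to falls found from Week 12 and should not be read as typical of the trial.

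It is tempting to say the true nadir is generally missed. The documents do not support that, since the usual nadir is sampled by schedule. A deeper unscheduled count, an unscheduled second fall, or a boy whose only below-LLN value is unscheduled can be lost from the tables, but these are possibilities. Nor is the net direction clear: longer recovery makes the drug look worse, while a missed nadir or second fall makes it look better. Extra retests would be expected mainly on givinostat from its known platelet effect, but that is inference, not trial data. SAP 2.8 also covers ECG values, but nothing here shows a comparable distortion of the QTcF outlier counts.

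This is worth correcting. It affects descriptive safety tables only.

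**What to change.** Add one sentence to SAP 5.2.1, carried into 5.2.2, or issue it as a further addendum: as an exception to Section 2.8, the minimum platelet count (maximum triglycerides), time to that value, time to recovery, time on treatment after or without recovery, and further decrease (increase) after recovery are derived from all post-baseline values, scheduled and unscheduled. Keep by-visit summaries, shift tables and plots on scheduled values. If the shells already specify all values for these tables, the sentence simply brings the SAP into line.

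The cost is the sentence and a change of input records in a few table programs. The retest values are already due to be listed under 2.8, so no new data are needed. No clinical rule changes.

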2.9 COVID-19

It is noted that particular attention may need to be given to the impact on key efficacy or safety assessments as a result of the COVID-19 pandemic. Consideration of the different areas of impact has been made as described below.

Protocol deviations related to COVID-19 will be recorded under separate categories indicating the type of deviation and that this was due to COVID-19. The assigned categories will be presented in the protocol deviation listing and table summary of major deviations as described in [Section 3.2](#).

Subjects who prematurely discontinue the study due to COVID-19 will record this as their reason for withdrawal and this will be included in the summary of reasons for withdrawal as described in [Section 3.1](#).

Subjects with a modification, interruption or who permanently stop IMP due to COVID-19 will record this as the reason for modification and this will be presented in the summary and listing of IMP modifications as described in [Section 3.5](#).

Missing efficacy data will be subject to the imputation and analysis methods described in [Sections 4.4.4.1](#) and [4.4.4.2](#). Missing data due to COVID-19 will be assumed to be Class 1 missing data (due to reasons other than being non-ambulatory or physically unable to perform the test / assessment) and handled accordingly. The tipping point analysis described in [Section 4.4.4.3](#) will assess the impact of the missing data on the primary analysis.

In order to provide supportive information for interpretation of the key efficacy and safety analyses, a summary of the number and percentage of subjects with missing assessments at each scheduled visit will be presented by treatment group and overall for the following selected data on the ITT analysis set in the target population (efficacy data) or safety analysis set in the overall population (safety data) as appropriate:

- All primary and key secondary efficacy assessments

- Clinical laboratory
- Vital signs
- Electrocardiogram
- Echocardiography
- Pulmonary function test

In addition, these summaries will be repeated to present the number and percentage of subjects with assessments completed outside of the expected protocol defined assessment window, at each scheduled visit by treatment group and overall. This summary will also include the number and percentage of subjects with assessments completed outside of the extended window for the 18 month assessment (+/-60 days) which was applied due to impact of the COVID-19 pandemic.

The COVID-19 pandemic has resulted in some subjects completing the EOS (18 month) assessment outside of the expected protocol defined assessment window or, additionally, outside of the extended +/-60 day window, which may have an impact in progressive disease. Therefore, a sensitivity analysis will be conducted on the ITT analysis set in the target population. The analysis described in Section 4.4.2 for each of the primary and key secondary endpoints will be repeated, excluding any subjects whose respective 18 month assessment was completed outside of the expected assessment window. In each case, the analysis will first exclude subjects where the 18 month assessment was outside of the protocol defined window and then will be repeated only excluding subjects where the 18 month assessment was outside of the +/-60 day window.

If these summaries and analyses suggest that further investigation is beneficial, additional summaries and/or analyses may be added post hoc to address missing data or assessments outside of protocol defined windows. This may include but is not limited to: additional sensitivity analyses of the efficacy endpoints, additional summaries of selected safety data for overall worst case post-baseline values, application of visit windows to group post-baseline data across multiple visits as appropriate.

2.10 Blinded Data Review Meeting

Italfarmaco will convene a blinded data review meeting (BDRM) after the data have been cleaned and before the study is locked and unblinded.

The BDRM will make decisions that will include, but not be limited to, the determination of whether protocol deviations are 'major' or 'minor', or not a protocol deviation at all. The definitions used to classify deviations as 'major' will be documented in the BDRM minutes.

